2.8.3 Laboratory data

Only "on-treatment" laboratory data (i.e. all assessments in the safety observation as defined in Section 2.1.1.4) will be summarized.

The summary of laboratory evaluations will be presented for three groups of laboratory tests (hematology, clinical chemistry, and urinalysis).

Descriptive summary statistics for the change from baseline to each study visit of interest will be presented. These descriptive summaries will be presented by laboratory test and treatment group. Change from baseline will only be summarized for patients with both baseline and post baseline values. In addition, shift tables using the low/normal/high/ (low and high) classification will be used to compare Baseline to the worst on-treatment value.

For urinalysis, frequency tables will be presented.

All laboratory data will be listed by center, subject number, and visit/time and if ranges are available, abnormalities will be flagged.

2.8.4 Other safety data

2.8.4.1 Vital signs

Only "on-treatment" vital signs data (i.e. all assessments in the safety observation as defined in Section 2.1.1.4) will be summarized.

Descriptive summary statistics for the change from baseline to each study visit of interest will be presented. These descriptive summaries will be presented by vital sign parameter and treatment group. Change from baseline will only be summarized for patients with both baseline and post baseline values. Note: As blood pressure will be assessed for both arms, the average of the available blood pressure assessments will be summarized/listed.

All vital signs data will be listed by center, subject number, and visit/time and if ranges are available, abnormalities will be flagged.

2.8.4.2 Immunogenicity

The number and percentage of patients without immunogenicity and with positive immunogenicity will be provided. The number and percentage of patients with neutralizing antibodies will be presented as well.

All immunogenicity results (anti-AIN457 antibodies) will be listed by treatment group, center, subject number, and study visit.

Page 33 of 53

QuantiFERON TB-Plus test

All QuantiFERON TB-Plus test results will be listed by treatment group, center, subject number, and study visit.

2.10 Patient-reported outcomes

The following secondary PRO endpoints will be analyzed according to treatment received (see Section 2.2 for further details) for the FAS:

- Change from Baseline in PGA VAS at Week 4, 8, 12, 16, 20, 24, 28, 36, 44 and 52
- Change from Baseline in FACIT-Fatigue at Week 4, 8, 12, 16, 20, 24, 28, 36, 44 and 52
- Change from Baseline in SF-36 at Week 4, 8, 12, 16, 20, 24, 28, 36, 44 and 52
- Change from Baseline in EQ-5D at Week 4, 8, 12, 16, 20, 24, 28, 36, 44 and 52

Descriptive summary statistics for the change as well as relative change from baseline of PGA VAS to each study visit of interest will be presented for each treatment group. Change from baseline will only be summarized for patients with both baseline and post baseline values.

Descriptive summary statistics for the change as well as relative change from baseline of FACIT-Fatigue to each study visit of interest will be presented for each treatment group. Change from baseline will only be summarized for patients with both baseline and post baseline values.

For SF-36, the following variables will be evaluated:

SF-36 domain scores

- SF-36 domain score responders
 - Type I responders (improvement of ≥ 5 points in ≥ 6 domains)
 - Type II responders (improvement of ≥ 10 points in ≥ 3 domains)
- SF-36 Physical Component Summary (PCS) and Mental Component Summary (MCS) scores (norm-based scores)
- SF-36 PCS and MCS score responders
 - Type I responders (improvement of ≥ 2.5 points)
 - Type II responders (improvement of ≥ 5 points)

Descriptive summary statistics for the change as well as relative change from baseline of SF-36 domain and summary scores to each study visit of interest will be presented for each treatment group. Change from baseline will only be summarized for patients with both baseline and post baseline values. The proportion of responders at each time point will be summarized descriptively for each treatment group.

The EQ-5D is a questionnaire with 5 questions (regarding mobility, self-care, usual activities, pain/discomfort, and anxiety/depression) each with 5 categories and a health state assessment from 0 (worst possible health state) to 100 (best possible health state). The number and percentage of patients in each of the 5 categories for each question will be presented by study visit and treatment group. Descriptive summary statistics will be provided for the change from baseline of health state assessment (known as EQ-5D-5L VAS) and EQ-5D-5L utility index (see Section 5.4.1 for further details) by study visit and treatment group.

2.11 Biomarkers

Not applicable.

2.13 Interim analysis

In total, 3 IAs will be conducted:

- IA1 after approx. 50% of patients reach Week 28
- IA2 after approx. 50% of patients reach Week 52
- IA3 100% of patients reach Week 28

The analyses for each of the aforementioned IAs are detailed in separate SAPs.

Prior to the protocol amendment version no. 2 including Amendment 2, the analyses of the primary endpoint and all other data at Week 28 were intended to be the final analysis of this study. As the blinded treatment period was extended until Week 52, this formerly final analysis will be conducted as IA3.

All IAs, in particular IA2 on Week 52 data will be informative to the planning of a Phase 3 program of secukinumab in GCA. There will be no multiplicity adjustment.

An independent unblinded study team will perform all interim analyses. Details will be specified in the Interim Analyses Charter.

3 Sample size calculation

Based on the observed response rates in the GIACTA study (Stone et al 2017), there were 56 out of 100 patients on tocilizumab every other week (56%) in combination with 26-week prednisolone taper regimen and 9 out of 51 patients treated with placebo (18%) in combination with 52-week prednisolone taper regimen. The expected observed responders in a sample size of 25 patients per treatment group is then 25*(56/100) = 14 and 25*(9/51) = 4. The posterior distribution of the expected difference in proportions was investigated for the sample size of 25 patients per treatment group.

Using an uninformative prior Beta (1, 1) for the secukinumab group and an informative prior for the expected observed responders in the placebo group of Beta (10, 43), 10000 Monte Carlo simulations of each posterior density was then computed and the posterior distribution of the difference then described using the 2.5, 50 (median) and 97.5 percentiles (Table 3-1).

Other plausible outcomes have been investigated if the observed response rates are different from expected (refer to Table 3-1).

Table 3-1 Sensitivity to changes in assumptions in observed response rates

Observed resp	Posterior quantiles for p1 – p2			Posterior	
Secukinumab (p1)	Placebo (p2)	2.5%	Median	97.5%	Prob(p1 > p2)
0.56	0.16	0.19	0.38	0.56	0.99
0.56	0.20	0.16	0.36	0.55	0.99
0.56	0.24	0.15	0.35	0.55	0.99

Observed resp	Posterior quantiles for p1 – p2			Posterior	
Secukinumab (p1)	Placebo (p2)	2.5%	Median	97.5%	Prob(p1 > p2)
0.56	0.28	0.13	0.34	0.54	0.99
0.52	0.16	0.14	0.34	0.53	0.99
0.48	0.16	0.11	0.31	0.51	0.99

4 Change to protocol specified analyses

The baseline prednisolone dose subgroup categories have been updated from > 40 mg/day and ≤ 40 mg/day to ≥ 40 mg/day and < 40 mg/day to align with the planned prednisolone taper regimen.

Sustained remission at a timepoint refers to patients being without flare until that timepoint and in adherence to the protocol prednisolone taper regimen. As adherence to the protocol prednisolone taper regimen is a component of the sustained remission definition already; any redundant mention of adherence to prednisolone taper regimen has been removed throughout this document.

Any reference to the time point after clinical remission has been updated to be after Baseline; this aligns more clearly with what was planned to be analyzed.

5 Appendix

5.1 Imputation rules

5.1.1 Study drug

Any partial dates will be imputed as follows:

- Take the earlier day of:
 - The last day in the month and
 - The end day of the corresponding epoch

5.1.2 Adverse event date imputation

5.1.2.1 Adverse event end date

For the purpose of date imputation, the study treatment follow-up period date is defined as the last available visit date, i.e. including unscheduled visits after the end of study visit.

- 1. If the AE end date month is missing, the imputed end date should be set to the earliest of the (study treatment follow-up period date, 31DECYYYY, date of death).
- 2. If the AE end date day is missing, the imputed end date should be set to the earliest of the (study treatment follow-up period date, last day of the month, date of death).
- 3. If AE year is missing or AE is ongoing, the end date will not be imputed.

If the imputed AE end date is less than the existing AE start date then use AE start date as AE end date.

5.1.2.2 Adverse event start date

Adverse events with completely missing onset dates will be considered to be treatment emergent. AEs with partially missing onset dates will also be included as treatment emergent when the month (if it exists) and the year occur on or later than the month and year of first administration of study treatment within this study.

Partial AE start dates are imputed with reference to the first administration of study treatment within this study as outlined in the table below.

The date value is split into day, month, year sections and referenced in the imputation table as outlined below.

	Day	Month	Year	
Partial AE Start Date	Not used	MON	YYYY	
Treatment Start Date	Not used	TRTM	TRTY	

The following matrix explains the logic behind the imputation.

Comparison of month section	MON missing	MON <trtm< th="">MON=TRTM	MON>TRTM	</trtm<>	MON=TRTM	MON>TRTM
YYYY missing	NC	NC	NC	NC
YYYY <trtm< td="">(D) =	(C) =	(C) =	(C) =	</trtm<>	(D) =	(C) =	(C) =	(C) =
	01JULYYYY	15MONYYYY	15MONYYYY	15MONYYYY
	Before Treatment Start	Before Treatment Start	Before Treatment Start	Before Treatment Start
YYYY=TRTY	(B) =	(C) =	(A)	(A)
	TRTSTD+1	15MONYYYY	= TRTSTD+1	= 01MONYYYY
	Uncertain	Before Treatment Start	Uncertain	After Treatment Start
YYYY>TRTY	(E) =	(A)	(A)	(A)
	01JANYYYY	= 01MONYYYY	= 01MONYYYY	= 01MONYYYY
	After Treatment Start	After Treatment Start	After Treatment Start	After Treatment Start

The following table is the legend to the logic matrix.

Relationship	
Before Treatment start	Partial date indicates AE start date prior to Treatment Start Date in this study
After Treatment start	Partial date indicates AE start date after Treatment Start Date in this study
Uncertain	Partial date insufficient to determine relationship of AE start date to Treatment Start Date in this study
Imputation calculation	
NC/Blank Uncertain	No convention
(A) After Treatment Start or Uncertain	MAX(01MONYYYY, TRTSTD+1)
(A) After Treatment Start or Uncertain	MAX(01MONYYYY, Treatment Start +1)
(C) Before Treatment Start	15MONYYYY

Relationship	
Before Treatment start	Partial date indicates AE start date prior to Treatment Start Date in this study
(D) Before Treatment Start	01JULYYYY
(E) After Treatment Start	01JANYYYY

Before imputing the AE start date, find the AE start reference date.

- If the AE end date is complete and the (imputed) AE end date < Treatment Start Date then AE start reference date = min (study informed consent date, earliest visit date).
- Else AE start reference date = Treatment Start Date

To impute AE start date:

- 1. If the AE start date year value is missing, the date uncertainty is too high to impute a rational date. Therefore, if the AE year value is missing, the imputed AE start date is set to NULL.
- 2. If the AE start date year value is less than the study treatment start date year value, the AE started before study treatment. Therefore:
 - a. If AE month is missing, the imputed AE start date is set to the mid-year point (01JULYYYY).
 - b. Else if AE month is not missing, the imputed AE start date is set to the mid-month point (15MONYYYY).
- 3. If the AE start date year value is greater than the study treatment start date year value, the AE started after study treatment. Therefore:
 - a. If the AE month is missing, the imputed AE start date is set to the year start point (01JANYYYY).
 - b. Else if the AE month is not missing, the imputed AE start date is set to the later of (month start point (01MONYYYY), AE start reference date + 1 day).
- 4. If the AE start date year value is equal to the study treatment start date year value:
 - a. And the AE month is missing the imputed AE start date is set to the AE reference start date + 1 day.
 - b. Else if the AE month is less than the study treatment start month, the imputed AE start date is set to the mid-month point (15MONYYYY).
 - c. Else if the AE month is equal to the study treatment start date month or greater than the study treatment start date month, the imputed AE start date is set to the later of (month start point (01MONYYYY), AE start reference date + 1 day).

If complete (imputed) AE end date is available and the imputed AE start date is greater than the (imputed) AE end date, then imputed AE start date should be set to the (imputed) AE end date.

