2.8.1 Adverse events

Adverse events will be coded by primary SOC and PT according to the MedDRA version 23.0 or later and will be presented for the whole study period. Only treatment emergent AEs (TEAEs) will be summarized.

Treatment emergent AEs are defined as events started after the first dose of study treatment or events present prior to the first dose of study treatment but increased in severity after dosing based on preferred term and within last dose + 84 days. For handling of missing or incomplete start and end dates, refer to Section 5.1.2.

Treatment emergent AEs will be summarized for each treatment group by presenting the crude incidence of patients having any TEAE and having a TEAE by primary SOC and by PT. Patients who experienced multiple AEs for a PT will be counted once for that PT, similarly for patients with multiple AEs per primary SOC. For summaries of TEAEs by severity, if a patient reports more than one AE with the same PT, only the AE with the maximum severity will be counted. Similarly, if a patient reports more than one AE within the same primary SOC, the event with the maximum severity will be counted for the SOC level. If the severity of a particular AE is missing, this severity will be treated as missing in summaries and listed accordingly.

The following TEAE information will be summarized separately by contingency tables:

- Adverse events, regardless of relationship to study or co-administered prednisolone treatment, by primary SOC and PT
- Adverse events, suspected to be related to study treatment, by primary SOC and PT

- Adverse events, suspected to be related to co-administered prednisolone treatment, by primary SOC and PT
- Serious AEs, regardless of relationship to study or co-administered prednisolone treatment, by primary SOC and PT
- Serious AEs, suspected to be related to study treatment, by primary SOC and PT
- Serious AEs, suspected to be related to co-administered prednisolone treatment, by primary SOC and PT
- Adverse events, regardless of relationship to study or co-administered prednisolone treatment, by primary SOC, PT and maximum severity (mild, moderate, severe)
- Adverse events leading to study treatment discontinuation, regardless of relationship to study or co-administered prednisolone treatment, by primary SOC and PT
- Adverse events leading to study treatment discontinuation, suspected to be related to study treatment, by primary SOC and PT

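### The SAP's treatment-emergent flag for AEs with missing or partial onset has no exception for an event known to have ended before the first dose

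*SAP*

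**What the plan says.** SAP 2.8.1 gives the definition: "Treatment emergent AEs are defined as events started after the first dose of study treatment", or events already present that became more severe after dosing, within 84 days of the last dose. It summarizes treatment-emergent AEs only, and sends incomplete dates to Section 5.1.2.

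SAP 5.1.2.2 opens with two flag sentences. The first: "Adverse events with completely missing onset dates will be considered to be treatment emergent". The second: "AEs with partially missing onset dates will also be included as treatment emergent when the month (if it exists) and the year occur on or" after those of the first dose. Neither mentions the end date.

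An imputation matrix and a set of numbered steps follow. Before the steps begin, a reference date is fixed, and here the end date does count: "If the AE end date is complete and the (imputed) AE end date < Treatment Start Date then AE start reference date" is moved back to the earlier of the consent date and the first visit date. Otherwise the reference date is the treatment start. The steps that matter are:

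- Year missing: "if the AE year value is missing, the imputed AE start date is set to NULL".
- First-dose year, month missing: "And the AE month is missing the imputed AE start date is set to the AE reference start date + 1 day".
- First-dose year, month equal to or later than the first-dose month: the later of the first of that month and the reference date plus one day.
- Closing cap, if the imputed start would fall after a complete end date: "then imputed AE start date should be set to the (imputed) AE end date".

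**The concern.** The steps show that the authors foresaw AEs that resolved before dosing. The flag sentences do not carry the same check. A record can therefore hold an imputed start before first dose and a treatment-emergent flag at once, and programmers could reasonably differ on which of the two drives the tables.

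Such records can occur. Protocol 7.1.1 collects AEs from informed consent, and Protocol 3.1 allows up to 6 weeks of screening, during which glucocorticoids may be given at the investigator's discretion. Because only treatment-emergent AEs are summarized, a wrong flag goes directly into the incidence tables that serve the safety objective.

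**Working it through.** This is date logic, and the plan states no figure to reproduce. The check applies the flag sentences and the numbered steps to the same records and compares both with the definition.

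**Worked record (illustrative dates).** Consent 25 April, taken as the earliest visit; first dose 20 May; AE end date 10 May, complete. The end precedes the first dose, so the reference date is 25 April.

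| Recorded onset | Flag sentences | Numbered steps | SAP 2.8.1 |
|---|---|---|---|
| Completely missing | Treatment-emergent | No date (NULL) | Not treatment-emergent |
| Year only, same year | Treatment-emergent | 25 April + 1 day = 26 April, pre-dose | Not treatment-emergent |
| May, day missing | Treatment-emergent | Later of 1 May and 26 April = 1 May, pre-dose | Not treatment-emergent |
| April, day missing | Not treatment-emergent | Mid-month, 15 April, pre-dose | Not treatment-emergent |

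The last column follows from the end date alone. An event over by 10 May cannot have started after 20 May and cannot have increased in severity after dosing, so it meets neither part of the definition.

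Rows two and three are a direct contradiction between flag and steps. In row one the steps are silent, so the flag conflicts only with the definition. In row four everything agrees.

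**The matrix.** For the May onset its formula gives the later of 1 May and 21 May, that is 21 May. The closing cap then applies: 21 May is after the end date, so the start becomes 10 May. That differs from the 1 May of the steps but is also before first dose, so the classification is the same.

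**Wider check.** The flag and the steps were coded and compared over every first-dose date in 2019, screening lengths of 7 to 42 days in weekly steps, and every same-year pre-dose end date consistent with a partial onset in the first-dose month or in the first-dose year with no month. In all 78,408 of 78,408 cases the flag said treatment-emergent while the steps imputed a start before first dose. This shows that the conflict is systematic for that type of record. It says nothing about how often such records arise.

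**Size.** Protocol 5.2 plans about 25 patients per arm. One wrongly flagged patient with no other event of that preferred term adds 1/25 = 4 percentage points to that term's crude incidence in the arm. If two or three such patients fell in the same arm and term, the addition would be 2/25 = 8 or 3/25 = 12 points.

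**The case against.** Counting an AE of unknown onset as treatment-emergent is a usual conservative convention. It applies equally to both arms, and SAP 2.8.1 itself delegates incomplete dates to Section 5.1.2. Protocol 7.1.1 asks for start and end dates, and Protocol 8.3 queries missing values, so few records should reach the analysis in this state. All of that stands and keeps the point small. It does not justify the flag here: the convention is for uncertain timing, and a complete end date before first dose removes the uncertainty that matters.

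Three stronger readings are tempting but not supported:

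- A reader might infer that resolved screening events in general enter the AE rates. They do not. Events with a full pre-dose onset date, or with a partial onset in a month or year before that of first dose, are correctly excluded.
- A reader might infer that the sentence on completely missing onsets contradicts the imputation steps. For those onsets the steps give NULL, so the conflict is only with the definition.
- A reader might infer from the matrix a further, treatment-emergent result for events already over before dosing. That overlooks the closing cap, which brings the start back to the pre-dose end date.

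**Conclusion.** The point holds as a narrow error in a stated rule. The two flag sentences lack an exception for a complete end date before first dose. For partial onsets in the first-dose month, or in the first-dose year with the month missing, this contradicts the section's own imputation steps; for completely missing onsets it contradicts the definition in SAP 2.8.1.

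The error can only add events. The rule is the same in both arms, so there is no evident reason for it to favour one. The 4-point figure assumes an arm of 25 and a patient with no other event of that preferred term. The number of affected records is not in the documents; that it is small is a judgement from how many conditions must coincide. Efficacy is untouched. This is a minor correction.

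**What to change.** Add one exception to both flag sentences in SAP 5.1.2.2: *unless the AE has a complete end date before the date of first administration of study treatment, in which case it is not treatment-emergent.* This aligns the flag with the steps and the definition, and leaves the conservative rule in place for onsets that are truly uncertain. The matrix need not be rewritten for this purpose, because the cap already yields a pre-dose start.

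The exception does not reach an incomplete end date that still lies clearly before first dose, such as an end in April with first dose on 20 May and no onset recorded. The team may wish to state how that case is handled.

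Cost: one clause in two sentences and one condition in the AE program.

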5.1.3 Concomitant medication date imputation

5.1.3.1 Concomitant medication end date

To impute concomitant end date:

- 1. If the concomitant end date year value is missing, the date uncertainty is too high to impute a rational date. Therefore, if the concomitant end year value is missing or ongoing, the imputed concomitant end date is set to NULL.
- 2. Else, if the concomitant end date month is missing, the imputed end date should be set to the earliest of the (study treatment follow-up period date, 31DECYYYY, date of death).
- 3. If the concomitant end date day is missing, the imputed end date should be set to the earliest of the (study treatment follow-up period date, last day of the month, date of death).

If the imputed concomitant end date is less than the existing concomitant start date, use the concomitant start date as the imputed concomitant end date.

